[REDACTED]

[REDACTED]

[REDACTED]

[REDACTED]

[REDACTED]

[REDACTED]

[REDACTED]

[REDACTED]

[REDACTED]

[REDACTED]

[REDACTED]

[REDACTED]

[REDACTED]

[REDACTED]

[REDACTED]

[REDACTED]

[REDACTED]

[REDACTED]

[REDACTED]	[REDACTED]	[REDACTED]	[REDACTED]	[REDACTED]	[REDACTED]	[REDACTED]	[REDACTED]	[REDACTED]
------------	------------	------------	------------	------------	------------	------------	------------	------------

[REDACTED]	[REDACTED]	[REDACTED]	[REDACTED]	[REDACTED]	[REDACTED]	[REDACTED]	[REDACTED]
------------	------------	------------	------------	------------	------------	------------	------------

[REDACTED]	[REDACTED]	[REDACTED]	[REDACTED]	[REDACTED]	[REDACTED]	[REDACTED]	[REDACTED]
------------	------------	------------	------------	------------	------------	------------	------------

[REDACTED]

[REDACTED]

[REDACTED]

[REDACTED]

[REDACTED]

[REDACTED]

[REDACTED]

[REDACTED]

[REDACTED]

[REDACTED]

[REDACTED]

[REDACTED]

[REDACTED]

[REDACTED]

[REDACTED]

[REDACTED]

[REDACTED]

[REDACTED]

[REDACTED]

[REDACTED]

[REDACTED]

[REDACTED]

[REDACTED]

[REDACTED]

[REDACTED]

[REDACTED]

[REDACTED]

[REDACTED]

[REDACTED]

[REDACTED]

[REDACTED]

[REDACTED]

[REDACTED]

[REDACTED]

[REDACTED]

[REDACTED]

[REDACTED]

[REDACTED]

[REDACTED]

[REDACTED]

[REDACTED]

[REDACTED]

[REDACTED]

[REDACTED]

[REDACTED]

[REDACTED]

[REDACTED]

[REDACTED]

[REDACTED]

[REDACTED]

[REDACTED]

[REDACTED]

[REDACTED]

[REDACTED]

[REDACTED]

[REDACTED]

[REDACTED]

[REDACTED]

[REDACTED]

[REDACTED]					[REDACTED]					
[REDACTED]										
[REDACTED]					[REDACTED]					
[REDACTED]	[REDACTED]	[REDACTED]	[REDACTED]	[REDACTED]	[REDACTED]	[REDACTED]	[REDACTED]	[REDACTED]	[REDACTED]	[REDACTED]
[REDACTED]	[REDACTED]	[REDACTED]	[REDACTED]	[REDACTED]	[REDACTED]	[REDACTED]	[REDACTED]	[REDACTED]	[REDACTED]	[REDACTED]
[REDACTED]	[REDACTED]	[REDACTED]	[REDACTED]	[REDACTED]	[REDACTED]	[REDACTED]	[REDACTED]	[REDACTED]	[REDACTED]	[REDACTED]

Origin [REDACTED]
[REDACTED]

[REDACTED]
[REDACTED]

[REDACTED]
[REDACTED]
[REDACTED]

[REDACTED]	[REDACTED]	[REDACTED]	[REDACTED]	[REDACTED]	[REDACTED]	[REDACTED]
[REDACTED]	[REDACTED]	[REDACTED]	[REDACTED]	[REDACTED]	[REDACTED]	[REDACTED]
[REDACTED]	[REDACTED]	[REDACTED]	[REDACTED]	[REDACTED]	[REDACTED]	[REDACTED]

[REDACTED]
[REDACTED]

[REDACTED]

[REDACTED]

[REDACTED]

[REDACTED]

[REDACTED]

[REDACTED]

[REDACTED]

[REDACTED]

[REDACTED]

[REDACTED]

[REDACTED]

[REDACTED]

[REDACTED]

[REDACTED]

[REDACTED]

[REDACTED]

[REDACTED]

[REDACTED]

[REDACTED]

[REDACTED]

[REDACTED]

[REDACTED]

[REDACTED]

[REDACTED]

[REDACTED]

[REDACTED]

[REDACTED]

[REDACTED]

[REDACTED]

[REDACTED]

[REDACTED]

[REDACTED]

[REDACTED]	[REDACTED]	[REDACTED]	[REDACTED]	[REDACTED]	[REDACTED]	[REDACTED]
[REDACTED]	[REDACTED]	[REDACTED]	[REDACTED]	[REDACTED]	[REDACTED]	[REDACTED]

[REDACTED]	[REDACTED]	[REDACTED]	[REDACTED]	[REDACTED]	[REDACTED]	[REDACTED]
------------	------------	------------	------------	------------	------------	------------

[REDACTED]

[REDACTED]

[REDACTED]

[REDACTED]

[REDACTED]

[REDACTED]

[REDACTED]	[REDACTED]	[REDACTED]	[REDACTED]	[REDACTED]	[REDACTED]	[REDACTED]	[REDACTED]	[REDACTED]
[REDACTED]	[REDACTED]	[REDACTED]	[REDACTED]	[REDACTED]	[REDACTED]	[REDACTED]	[REDACTED]	[REDACTED]
[REDACTED]	[REDACTED]	[REDACTED]	[REDACTED]	[REDACTED]	[REDACTED]	[REDACTED]	[REDACTED]	[REDACTED]
[REDACTED]	[REDACTED]	[REDACTED]	[REDACTED]	[REDACTED]	[REDACTED]	[REDACTED]	[REDACTED]	[REDACTED]

[REDACTED]

[REDACTED]

[REDACTED]

[REDACTED]

[REDACTED]

[REDACTED]

[REDACTED]

[REDACTED]

[REDACTED]

[REDACTED]

[REDACTED]

[REDACTED]

[REDACTED]

[REDACTED]

[REDACTED]

[REDACTED]

[REDACTED]

[REDACTED]

[REDACTED]

[REDACTED]

[REDACTED]

[REDACTED]

[REDACTED]

[REDACTED]

[REDACTED]

[REDACTED]

[REDACTED]

[REDACTED]

[REDACTED]

[REDACTED]

[REDACTED]

[REDACTED]	[REDACTED]	[REDACTED]	[REDACTED]	[REDACTED]	[REDACTED]	[REDACTED]	[REDACTED]	[REDACTED]	[REDACTED]	[REDACTED]	[REDACTED]	[REDACTED]
[REDACTED]	[REDACTED]	[REDACTED]	[REDACTED]	[REDACTED]	[REDACTED]	[REDACTED]	[REDACTED]	[REDACTED]	[REDACTED]	[REDACTED]	[REDACTED]	[REDACTED]
[REDACTED]	[REDACTED]	[REDACTED]	[REDACTED]	[REDACTED]	[REDACTED]	[REDACTED]	[REDACTED]	[REDACTED]	[REDACTED]	[REDACTED]	[REDACTED]	[REDACTED]

[REDACTED]

- [REDACTED]
- [REDACTED]
- [REDACTED]

[REDACTED]

[REDACTED]

[REDACTED]

[REDACTED]

[REDACTED]	[REDACTED]	[REDACTED]	[REDACTED]	[REDACTED]	[REDACTED]	[REDACTED]	[REDACTED]	[REDACTED]	[REDACTED]
[REDACTED]	[REDACTED]	[REDACTED]	[REDACTED]	[REDACTED]	[REDACTED]	[REDACTED]	[REDACTED]	[REDACTED]	[REDACTED]
[REDACTED]	[REDACTED]	[REDACTED]	[REDACTED]	[REDACTED]	[REDACTED]	[REDACTED]	[REDACTED]	[REDACTED]	[REDACTED]

[REDACTED]

[REDACTED]

[REDACTED]

[REDACTED]

[REDACTED]

[REDACTED]

[REDACTED]

[REDACTED]	[REDACTED]	[REDACTED]	[REDACTED]	[REDACTED]	[REDACTED]	[REDACTED]	[REDACTED]	[REDACTED]
[REDACTED]	[REDACTED]	[REDACTED]	[REDACTED]	[REDACTED]	[REDACTED]	[REDACTED]	[REDACTED]	[REDACTED]
[REDACTED]	[REDACTED]	[REDACTED]	[REDACTED]	[REDACTED]	[REDACTED]	[REDACTED]	[REDACTED]	[REDACTED]

[REDACTED]

[REDACTED]

[REDACTED]

[REDACTED]

[REDACTED]

[REDACTED]	[REDACTED]	[REDACTED]	[REDACTED]	[REDACTED]	[REDACTED]
[REDACTED]	[REDACTED]	[REDACTED]	[REDACTED]	[REDACTED]	[REDACTED]
[REDACTED]	[REDACTED]	[REDACTED]	[REDACTED]	[REDACTED]	[REDACTED]

[REDACTED]

[REDACTED]

[REDACTED]

[REDACTED]

[REDACTED]

[REDACTED]

[REDACTED]

[REDACTED]

[REDACTED]

[REDACTED]

[REDACTED]

[REDACTED]

[REDACTED]

[REDACTED]

[REDACTED]

[REDACTED]

[REDACTED]

[REDACTED]

[REDACTED]

[REDACTED]

[REDACTED]

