[REDACTED] Additional study visits may be requested at the discretion of the PI. If the patient's dose is escalated, blood will be drawn approximately 1 week later [REDACTED] for safety laboratory and PD biomarker assessments.

During the Extension Period, patients who were de-escalated from the final tolerated dose for reasons other than safety or PK considerations may be re-escalated up to their maximally tolerated dose. After dose escalation is complete, the patient can be returned to a prior dose based on the patient's clinical status at the discretion of the treating physician after consultation with the SRC.

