4.3. Safety

The safety of ORGN001 (formerly ALXN1101) will be assessed based on:

- Incidence and severity of adverse events (AEs) and serious adverse events (SAEs)
- Incidence of clinical laboratory abnormalities
- Change from baseline in clinical laboratory assessments
- Change from baseline in clinical findings from physical examination
- Change from baseline in vital sign measurements
- Change from baseline in electroencephalogram (EEG) results

In order to monitor subject safety, data will be reviewed daily by the PI or designee during the first 2 weeks following initiation of ORGN001. [REDACTED]

The SRC [REDACTED] will review all available clinical data [REDACTED] prior to each subject's scheduled dose escalations in conjunction with the data monitoring committee (DMC) [REDACTED] and at any other time during the study as requested by the PI or Sponsor.

Based on the review of the available data, [REDACTED] the SRC, in consultation with the DMC, may recommend stopping, increasing, decreasing, or maintaining (current dose) the dose of ORGN001.

In addition to the scheduled dose escalations, the PI may also convene the SRC for unscheduled dose adjustments based on drug-related AEs and changes in clinical parameters. The SRC chair will also convene the DMC if a dose escalation is being considered or will notify the DMC if the dose is decreased. Blood and urine samples will be collected for PD and PK assessments on the first day the adjusted dose is administered. PD and safety laboratory assessments will be repeated [REDACTED] at the [REDACTED] follow-up visit.

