6.5.4. Other Safety Analyses

6.5.4.1. Analyses for Laboratory Tests

Descriptive statistics by visit will be presented for each laboratory parameter and for changes from baseline.

Serum Chemistry	Hematology	Coagulation	Urinalysis
Sodium	Red blood cell count	Prothrombin time	Specific gravity
Potassium	Mean corpuscular volume	International Normalized Ratio	pH
Bicarbonate	Mean corpuscular hemoglobin		Glucose
Chloride	Mean corpuscular hemoglobin concentration		Protein
Blood urea nitrogen	White blood cell count		RBC (by dipstick)
Creatinine	Neutrophils (absolute and percentage)		Ketones (by dipstick)
Calcium	Lymphocytes (Absolute and percentage)		Urine protein to creatinine ratio
Alanine aminotransferase	Monocytes (absolute and percentage)		
Aspartate aminotransferase	Eosinophils (absolute and percentage)		

Serum Chemistry	Hematology	Coagulation	Urinalysis
Alkaline phosphatase	Basophils (absolute and percentage)		
Total bilirubin	Platelet count		
Serum osmolality	Hemoglobin		
Total Serum Albumin	Hematocrit		

For purposes of analyses, laboratory results based upon standardized units will be used. All laboratory values, where applicable, will be classified as normal, below normal, or above normal, and shift tables will be presented over time.

Scatter plots of all chemistry and hematology lab test values [REDACTED] by baseline values will be plotted. For hematology, the following tests will be plotted: RBC, WBC count, platelet count, hemoglobin, and hematocrit. All data will be presented in by-subject listings and flag for abnormal result will be included.

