8.5. Visit Windows

Visits will be assigned to visit windows. Data is summarized according to the visit windows reported in the following table when appropriate (e.g., laboratory parameters, vital signs,

¹ Additional WHO growth chart information and methodology can be found at http://www.who.int/childgrowth/publications/technical_report_2/en/index.html.

² The SAS macro and user instructions can be found at <https://www.who.int/childgrowth/software/en/>.

³ Additional CDC growth chart information and methodology can be found at https://www.cdc.gov/growthcharts/clinical_charts.htm.

[figure not shown]
⁴ The SAS macro and user instructions can be found at <https://www.cdc.gov/nccdphp/dnpao/growthcharts/resources/sas.htm>.

[figure not shown]
developmental assessments, etc.). If multiple assessments occur within a visit window, the assessment closest to the target day will be used. In case of ties, with an equal number of days on either side of the target day, the value from the day before the target day shall be used.

[figure not shown]
██████	██████████████████
██████████████	██████
██████	█████
██████	█████
██████	█████
██████	█████
██████	█████
██████	█████
██████	█████
██████	█████
██████████	█████
██████	█████
██████	█████
██████	█████
██████	█████
██████	█████
██████	█████
██████	█████
██████	█████
██████	█████
██████	█████
██████	█████
██████	█████
██████	█████
██████	█████
██████	█████
██████	█████
██████	█████
██████	█████
██████	█████
██████	█████
██████	█████
██████	█████
██████	█████

██
██████

[figure not shown]
█████ ██
██

[figure not shown]

[figure not shown]

[figure not shown]

[figure not shown]

[figure not shown]

[figure not shown]

[figure not shown]

[figure not shown]

[REDACTED]

[REDACTED]

[REDACTED]

[REDACTED]

[REDACTED]

[REDACTED]

[REDACTED]

[REDACTED]

[REDACTED]

[REDACTED]

[REDACTED]

[REDACTED]

[REDACTED]

[REDACTED]

[REDACTED]

[REDACTED]

[REDACTED]

[REDACTED]

[REDACTED]

[REDACTED]

[REDACTED]

[REDACTED]

[REDACTED]

[REDACTED]

[REDACTED]

[REDACTED]

[REDACTED]

[REDACTED]

[REDACTED]

[REDACTED]

[REDACTED]

[REDACTED]

[REDACTED]

[REDACTED]

[REDACTED]

[REDACTED]

[REDACTED]

[REDACTED]

[REDACTED]

[REDACTED]

[REDACTED]

[REDACTED]

[REDACTED]

[REDACTED]

[REDACTED]

[REDACTED]

[REDACTED]

[REDACTED]

[REDACTED]

[REDACTED]

[REDACTED]

[REDACTED]

[REDACTED]

[REDACTED]

[REDACTED]

[REDACTED]

[REDACTED]

[REDACTED]

[REDACTED]

[REDACTED]

[REDACTED]

[REDACTED]

[REDACTED]

[REDACTED]

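### The incidence of laboratory abnormalities is a named safety endpoint, but the readable plan has no per-patient count of it, and the visit-window rule can only understate such a count.

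*SAP*

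**What the plan says.** The safety endpoints in Protocol 2.2.1 and SAP 4.3 include "Incidence of clinical laboratory abnormalities". Change from baseline in laboratory values is a separate item in both lists. Protocol 2.2 asks for the endpoints over the first 6 months and over the whole treatment period. Safety over the first 6 months is the primary objective (Protocol 2.1.1).

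The analysis text offers the following for laboratory data:

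- SAP 6.5.4.1: "Descriptive statistics by visit will be presented for each laboratory parameter and for changes from baseline".
- SAP 6.5.4.1: "All laboratory values, where applicable, will be classified as normal, below normal, or above normal, and shift tables will be presented over time". Protocol 13.8.2 describes these shift tables as by visit.
- SAP 6.5.4.1 also plans scatter plots against baseline and by-subject listings with a flag on abnormal results.

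SAP 8.5 then sets the record-selection rule. Its scope is given as: "Data is summarized according to the visit windows reported in the following table when appropriate (e.g., laboratory parameters, vital signs". Within a window, "If multiple assessments occur within a visit window, the assessment closest to the target day will be used". If two values are equally distant from the target, "the value from the day before the target day shall be used". No exception for abnormality counts and no rule for unscheduled results can be read there. SAP 3.1 records no change from the protocol's analyses.

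**The concern.** An incidence endpoint needs a patient-level numerator: how many patients had at least one abnormal value after baseline. The readable tables do not produce it. The selection rule also ignores whether a value is abnormal, so an abnormal result can give way to a normal one that lies nearer the target day or falls earlier in a tie.

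The results most exposed are those taken outside the regular calendar. Protocol 12.3 requires safety laboratory tests seven days after an unscheduled dose adjustment or a return to a prior dose. It also leaves follow-up of abnormal results to the investigator, so repeat draws are foreseeable. These are samples for which a safety reader would want the worst value. At stake is whether the report's summary tables answer a stated endpoint that serves the primary objective.

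**Working it through.** The documents give no incidence, power or sample-size figure that bears on this point, so there is nothing of theirs to reproduce. The check has three steps.

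**Step 1. Can the planned tables give a patient incidence?** Take the planned minimum of 4 patients (Protocol 13.2). Suppose the shift tables for one parameter show one patient shifted to high at one visit and one patient shifted to high at another.

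- If it is the same patient, the incidence is 1/4 = 25%.
- If they are different patients, it is 2/4 = 50%.

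The by-visit tables look the same in both cases. In general, if visit *v* shows *a_v* abnormal patients out of *N*, the incidence lies between max(*a_v*)/*N* and min(Σ*a_v*, *N*)/*N*, and the tables do not say where. This gap exists even if no value is ever dropped.

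**Step 2. Which way does the window rule push?** The values kept under SAP 8.5 are a subset of all values. Any patient who is abnormal on a kept value is also abnormal on the full set, and the reverse need not hold. So:

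incidence from kept values ≤ incidence from all values.

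The two are equal when no window holds more than one value. Otherwise the error can only be an undercount. A patient is lost only if every abnormal value of that patient is dropped.

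**Step 3. How large could it be?** The window table is redacted, so the number of dropped values cannot be derived. One missed patient at *N* = 4 changes the incidence by 1/4 = 25 percentage points.

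For scale only, assume independent assessments, each abnormal with probability *p*, with 13 kept values per patient and *d* dropped. None of these assumptions is in the documents. The 13 is borrowed from the visit columns legible in Protocol Table 4, which need not all carry laboratory draws. The chance of ever being abnormal is 1 − (1 − *p*)^13 on kept values and 1 − (1 − *p*)^(13 + *d*) on all values.

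| *p* | kept only | all, *d* = 1 | all, *d* = 4 | undercount (points) |
|---|---|---|---|---|
| 0.02 | 23.1% | 24.6% | 29.1% | 1.5 to 6.0 |
| 0.05 | 48.7% | 51.2% | 58.2% | about 2.5 to 9.5 |
| 0.10 | 74.6% | 77.1% | 83.3% | 2.5 to 8.7 |

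With *d* = 0 the undercount is zero in every row.

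**The case against.** The strongest reply has four parts.

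**The escalation draws are scheduled.** A reader might infer that the rule routinely discards the samples taken about 3 days before each escalation and those for which, after it, "blood will be drawn approximately 1 week later" (Protocol 3.3). The documents do not support that. These are planned visits. The infusion row of Protocol Table 4 repeats a three-visit pattern four times and then has one final visit, which fits a separate visit before, at and after each escalation. If each has its own window, these values are kept. The redacted table could show this either way. This objection stands, and it limits the selection problem to repeat and unscheduled results.

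**The rule is qualified.** SAP 8.5 applies windows where appropriate, and SAP 6.5.4.1 speaks of classifying all laboratory values. That nearest-value selection feeds the abnormality tables is therefore an inference, though a natural one, since laboratory parameters are SAP 8.5's own first example. The missing patient count in step 1 does not depend on it.

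**Abnormal results are visible elsewhere.** A reader might infer that abnormalities would vanish from the report. They would not. SAP 6.5 and 6.5.4.1 put all laboratory data in listings with abnormal results flagged, and with about 4 patients the incidence could be rebuilt by hand. Results judged clinically significant are to be recorded as adverse events (Protocol 12.5.1), and those are counted by patient. This stands as mitigation. It does not close the gap. Under Protocol 12.5.1 a repeat test does not count as additional diagnostic testing, so an abnormal value followed only by a normal repeat need not become an adverse event unless another condition is met. Adverse event tables also count preferred terms, not low or high values per parameter.

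**Redacted appendices may hold the table.** This cannot be excluded. However, the analysis text of SAP 6.5.4.1 is nearly intact and mentions no such count.

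The point also does not extend to vital signs, whose only named endpoint is change from baseline.

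**Conclusion.** The point holds as a specification gap of modest severity. In the readable text, a named safety endpoint has no matching per-patient summary. That finding needs no assumption beyond the absence of such a table from the redacted pages.

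The window rule is a secondary problem. Its direction is certain: a count drawn from windowed values is equal to or below the true count. Its size is unknown, and it is zero if no window holds two values for the same patient. One missed patient would be 25 percentage points at the minimum sample of 4. The illustrated range of 1.5 to 9.5 points per parameter for one to four dropped values rests on assumed inputs and only gives an order of magnitude. The documents do not show that any abnormal value will in fact be dropped. The change is worth making because it costs little and the endpoint serves the primary objective.

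**What to change.** In SAP 6.5.4.1 add, for each laboratory parameter:

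- the number and percentage of patients with any low and with any high post-baseline value;
- a shift from baseline to the worst post-baseline value.

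Base both on all scheduled and unscheduled results. Present them for the first 6 months and for the whole treatment period, to match Protocol 2.2. In SAP 8.5, state that the closest-to-target rule and its tie rule apply to by-visit summaries only.

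The cost is two extra tables from data already planned for collection, with no new visits or samples. The abnormality counts may look slightly less favourable than the by-visit tables suggest.
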